B. Statistical Considerations

B.1. Sample Size Justification:

Our sample sizes were chosen based on an iterative process involving determining the size of the target population eligible, feasibility constraints, and then verifying adequate power to test the hypotheses across all of our proposed studies for Projects 1-5. Through these detailed considerations, and input from our expert statisticians, we have been able to verify adequate power to address all of our study aims with the proposed sample sizes for the SAGES I SELECT subsample (N=148), the SAGES II cohort (N=460) and the SAGES II subsample (N=180). Power has similarly been verified for all aims of each project. For SAGES II, approximately 50% of the cohort will be enrolled at BIDMC and 50% at BWH. The data, however, will be analyzed together. Computations allow for two-sided type-I error probability 0.05 and to take into account cumulative attrition consistent with our experience in this population. We use multiple imputation to account for missing data where appropriate.

B.1.2. Experimental design and sampling: general considerations

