Aim 2. To relate neurophysiology measures 2 months and 12 months after hospitalization with changes in cognitive performance and cognitive decline in SAGES II patients with versus without delirium. Power calculations: We estimate that 50 patients (25 normal, 25 MCI) will develop delirium; the comparison

sample will also contain 50 patients, an anticipated 20 with MCI. We assume a dropout rate of 5% (based on prior work), leading to a total of 95 participants with evaluable data; this will provide 80% power to detect a standardized difference of 0.62 SD between the delirious and non-delirious samples, which is consistent with the minimum observed in our pilot study. For the regression of changes in cortical physiology measures with change in the GCP, we would have greater than 80% power to detect an R² of 0.10 or greater. For the long-term follow-up measure, assuming cumulative loss to follow-up of 10% over one year, we anticipate observing the 18-month trajectory of change for 83 patients, providing 80% power to detect partial R^2 of 0.12 or greater in a multivariate model with adjustment for up to 12 covariates. In prior work by our group, the R² between TMS plasticity measures and cognition in patients with Diabetes was 0.30.³ In other pilot work, we found that the R² between EEG relative power and measures of attention and working memory in patients with AD was 0.42. Together, these results suggest we will have adequate power for our Aims. Aim 3. To characterize differences in neurophysiology metrics as a function of history of delirium and cognitive decline, and to correlate these measures with long term cognitive outcomes. Power Calculations: The sample (N=128) is sufficient to provide 80% power to detect a between-group difference of 0.53 standard deviation (SD) units. Thus, we will have sufficient power to detect effects that are more subtle than observed in our pilot analyses, and that have been associated with clinically meaningful relationships with cognition in our preliminary work and in work by other groups.^{2,3,14,98}

B.2. Data Analysis

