Aim 2 Analyses: The primary goal of this analysis is to assess the degree to which patients with delirium (approximately 50 anticipated) have a decrease in rs-EEG high-frequency power and abnormal TMS measures of reactivity, connectivity and plasticity. We further seek to quantify the degree to which these cortical physiology changes are associated with the magnitude of perturbations in cognitive functioning attending the delirium episode (as indexed by the GCP score 1 month after surgery), as well as subsequent cognitive decline 18 months after hospitalization. In order to establish that changes in cortical physiology may be associated with delirium rather than hospitalization or surgery, we will assess post-operative changes in the same measures in a comparison sample of 50 participants without delirium. We will identify changes in cortical physiology measures using a mixed effects linear regression model, with stimulation session as the within-subject factor and occurrence of delirium as the second factor. Subsequently, to evaluate whether patients with greater short-term cognitive decline have more severe abnormalities in cortical physiology, cognitive status one month after the delirium episode (as measured via the GCP Score) will be correlated with the changes in cortical physiology measures via multiple regression methods. In conjunction with data core statisticians, we will then apply mixed effects regression models to characterize the adjusted mean GCP scores and the trajectory of scores over time, with the prediction that cortical physiology measured at 2 months post-hospitalization will predict cognitive outcomes 18 months after hospitalization.

Aim 3 Analyses: The primary goal of this analysis will be to examine how the presence or absence of a history of delirium relates to subsequent cortical physiology measures at around 4 years after the index hospitalization, and the degree to which these factors predict subsequent long-term cognitive decline. We hypothesize that SAGES I patients with a history of delirium will have abnormalities on the cortical physiology measures (baseline power and EEG connectivity, TMS reactivity, connectivity AND plasticity) relative to those without. We also hypothesize that cortical physiology measures will be correlated with the magnitude of cognitive decline since the index hospitalization. These hypotheses

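### Project 5 Aim 2 asks about short-term cognitive decline and is powered for change in GCP, but its analysis text names the one-month GCP level and commits to no baseline adjustment

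*Protocol*

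**What the plan says.** Protocol section B.2.3, Project 5, Aim 2 Analyses, states the purpose of the regression as "to evaluate whether patients with greater short-term cognitive decline have more severe abnormalities in cortical physiology". The same sentence then gives the cognitive variable: "cognitive status one month after the delirium episode (as measured via the GCP Score) will be correlated". The other variable is the change in the physiology measures, and the method named is multiple regression. Earlier in that paragraph the cognitive perturbation that goes with the delirium episode is described "as indexed by the GCP score 1 month after surgery". Both places name a single post-operative score. Neither subtracts a baseline score, and no covariate is listed for this regression.

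Section B.1.3, Project 5, Aim 2, gives the power for a different variable: "For the regression of changes in cortical physiology measures with change in the GCP". The claim attached to that regression is that "we would have greater than 80% power to detect an R² of 0.10 or greater". The sample there is described as "leading to a total of 95 participants with evaluable data".

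The SAGES II baseline interview (section A.4.4) includes the neuropsychological battery for the whole cohort, so a pre-operative GCP score is available.

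**The concern.** The aim and the power statement concern change, while the analysis text concerns a level. A one-month GCP score is the sum of where the patient started and how far the patient moved. Section B.1.3 expects a cognitively mixed sample: 25 of the 50 patients with delirium and 20 of the 50 comparison patients are expected to have MCI. Differences in starting level are therefore likely to be a visible part of the one-month score.

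Two things are at stake. First, a correlation with the unadjusted level cannot be read as a correlation with decline, because it may reflect prior ability. Second, the power claim was made for another variable and does not carry over automatically.

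**Working it through.** **Inputs from the protocol.** Evaluable n = 95 and R² = 0.10 (B.1.3, Project 5, Aim 2). On alpha, section B.1 says "Computations allow for two-sided type-I error probability 0.05".

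**Assumed inputs.** ρ is the correlation between baseline and one-month GCP, with equal SDs at the two times. The protocol gives no value, so a range is shown. In steps 2 and 3, physiology change is taken as uncorrelated with baseline GCP.

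**Step 1: reproduce the stated power, for change in GCP.** Use an F test of one predictor with noncentrality λ = n·R²/(1 − R²) = 95 × 0.10/0.90 = 10.56. Power is 0.895 (Fisher z approximation 0.881). The claim of more than 80% holds for change.

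**Step 2: same true effect, unadjusted one-month level.** In units of the GCP SD, change has SD √(2(1 − ρ)). If physiology change is unrelated to baseline GCP, its covariance with the one-month level equals its covariance with change. Hence

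corr(physiology change, level) = √0.10 × √(2(1 − ρ)), and R² for the level = 0.20 × (1 − ρ).

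**Step 3: same true effect, one-month GCP with baseline GCP as a covariate.** The partial R² = 0.20(1 − ρ)/(1 − ρ²) = 0.20/(1 + ρ).

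| ρ (assumed) | R², level only | Power, level only | Partial R², baseline as covariate | Power, baseline as covariate |
|---|---|---|---|---|
| 0.5 | 0.100 | 0.895 | 0.133 | 0.966 |
| 0.6 | 0.080 | 0.812 | 0.125 | 0.954 |
| 0.7 | 0.060 | 0.683 | 0.118 | 0.941 |
| 0.8 | 0.040 | 0.504 | 0.111 | 0.926 |
| 0.9 | 0.020 | 0.281 | 0.105 | 0.911 |

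Power for the level alone falls below 80% once ρ exceeds about 0.61. It falls below half of 0.895 only once ρ exceeds about 0.83.

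**Step 4: attach the R² of 0.10 to baseline-adjusted change instead of simple change.** The R² for the level is then 0.10 × (1 − ρ²), which is 0.051, 0.036 and 0.019 at ρ = 0.7, 0.8 and 0.9. Power is 0.61, 0.46 and 0.27. The pattern is the same, but the protocol's power text refers to change, so the table above is the closer match.

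**Step 5: relax the assumption about baseline.** Let physiology change correlate with baseline GCP at k. The correlation with the level becomes k + √0.10 × √(2(1 − ρ)). At ρ = 0.8 the second term is 0.20.

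- k = +0.1: correlation 0.30, level-only power 0.858.
- k = −0.1: correlation 0.10, level-only power 0.163.
- No relation to change at all but k = 0.2: the correlation with the level is 0.20, and the test is significant about 50% of the time although change plays no part.

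**The case against.** The strongest reply is that the analysis is not stated to be unadjusted. Aim 2 specifies multiple regression. The Aim 1 paragraph of Project 5 lists baseline cognitive function among the control variables for multivariable models, Aim 3 adjusts for it, and section B.2.1 sets a general rule for choosing confounders. A full covariate list can be left to a statistical analysis plan. With baseline GCP in the model, the regression does address decline. This shows that adjustment is permitted and perhaps intended. It does not remove the conflict, because the point is the named variable: the Aim 2 text names the level twice where the power text names change, and it does not commit to baseline adjustment.

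It is also fair to say that the question is secondary within Aim 2, after the comparison of physiology between patients with and without delirium. The 18-month analysis uses the trajectory of scores and is not affected.

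A reader might go further in three ways that the protocol does not support:

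- **That the analysis loses most of its power.** This needs ρ above about 0.83, no offsetting correlation between physiology change and baseline GCP, and no baseline covariate. The protocol establishes none of these. At ρ = 0.5 nothing is lost, and step 5 shows that power can move either way.
- **That the pre-operative GCP gap between delirium groups in section B.1.2 measures the confounding here.** That figure is for SAGES I before matching. Aim 2 uses a SAGES II subsample, so the figure cannot be carried over. In addition, the physiology variable is a change, and nothing in the protocol says that patients with low GCP change more.
- **That Aim 1 hypothesis H1B has the same fault.** It also uses one-month cognitive status, but its own paragraph lists baseline cognitive function as a control and stratifies by MCI against normal baseline cognition.

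**Conclusion.** The inconsistency stands. In Project 5 Aim 2 the analysis text names the one-month GCP level, while the stated question is decline and the power is computed for change. Taken as written and without baseline adjustment, the regression does not isolate short-term decline, and the stated power does not necessarily apply to it.

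The size of any power loss cannot be fixed from the protocol. Level-only power runs from 0.90 at ρ = 0.5 to 0.28 at ρ = 0.9, against 0.97 to 0.91 with baseline GCP as a covariate. This assumes equal SDs, R² = 0.10 for change, n = 95, and physiology change unrelated to baseline GCP. The problem of interpretation does not depend on ρ in the same way. It arises whenever physiology change is related to starting ability, which the protocol neither shows nor rules out.

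This is a free improvement: it aligns two sections and removes an avoidable ambiguity.

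**What to change.** In section B.2.3, Project 5, Aim 2 Analyses, state that the cognitive variable for the short-term regression is one-month GCP with baseline GCP as a covariate, or change in GCP from baseline. Describe the index of the perturbation earlier in that paragraph in the same way. Name one of the two, because they can give different answers if physiology change is correlated with baseline GCP. Either choice brings the analysis into line with the question and with the change-based power text in B.1.3.

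The cost is one sentence. Baseline cognition is already measured in every SAGES II participant, and no change to sample size or visits is needed. Under the assumptions above, power stays at about 0.90 for change and at 0.91 or more with the covariate, for ρ from 0.5 to 0.9.

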This study uses observational, prospectively collected cohort data for SAGES I and II. In specific cases, participants experiencing delirium during the index hospitalization will be matched to those without delirium on the basis of age and other factors. To obtain the probability sample of 148 existing SAGES I participants, a matched sampling procedure was piloted. This approach selects all SAGES I participants who had delirium during their index hospitalization and a sample of the non-delirious frequency-matched to the delirious on general cognitive performance (GCP) and age, both key predictors of long term cognitive decline (LTCD). We anticipate enrolling 74 participants with delirium during index hospitalization, and a corresponding 74 participants without. The nondelirious set will be chosen to have a similar distribution to those with delirium on a propensity score derived from a predictive model for delirium, taking into account SAGES I baseline GCP, age, and their interaction. To demonstrate the feasibility and validity of this approach, we conducted a pilot study that constructed 1001 such matched samples, and estimated the standardized mean difference (delirious minus nondelirious) on GCP, age and Charlson comorbidity index for each. While delirious patients in SAGES I were older, had lower GCP, and greater comorbidity than the nondelirious, the frequency matching effectively eliminated these imbalances. Pre-operative standardized mean difference in GCP score was -0.58; after matched selection, the difference decreased to -0.06 (95% CI: -0.13 to 0.011). For age, the pre-operative difference decreased from 0.29 to -0.04 (-0.16, 0.09) after matching. Likewise for the Charlson, the difference was reduced from 0.18 to 0.09 (-0.05, 0.26). These pilot data demonstrate the feasibility and effectiveness of this approach in reducing potential confounding bias, even for unmatched variables. Of

note, we originally powered analyses for a SAGES I probability sample size of 128 (64 per group) and SAGES II sample size of 400. Because we have expanded the sample sizes (to 148 and 460, respectively) and because power increases with sample size, we expect to exceed the estimated power described in the following sections.

B.1.3. Power by Project:

Project 1

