will be tested with general linear mixed-effects models controlling for differences in cortical physiology markers (transformed to approximate normality, if indicated). Because patients in SAGES I will have their physiology measurements measured at different timepoints following delirium, we will incorporate time since the index hospitalization as a covariate in the model in order to assess dynamic aspects of the association between delirium and downstream changes in cortical physiology. Participants will be matched by gender and age between the groups with and without delirium. Additional statistical adjustment will be made for index surgical procedure, baseline cognitive function, comorbidity, and vascular risk. Patients will be followed for a minimum of 8 years after initial enrollment in SAGES I (and 4 years after the TMS sessions), and cognitive function and progression to dementia tracked by the Core B team. We will use the same modeling approach to identify the degree of association between neurophysiology metrics and the magnitude of subsequent cognitive decline.

C. Subject Selection

C.1.This study involves two different prospective observational cohorts: Successful Aging after Elective Surgery I (SAGES I) and SAGES II.

C.1.1. SAGES I cohorts

SAGES I Cohort (N=560). Eligibility criteria for this cohort, assembled during the first cycle of the Program Project grant (PPG) is described under A.3.1.

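### Project 5 Aim 3 leaves sex out of its covariate list on the strength of a gender match that the SAGES I SELECT sampling does not provide

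*Protocol*

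**What the plan says.** Project 5 Aim 3 compares cortical physiology, measured around four years after surgery, between patients with and without earlier delirium: "We hypothesize that SAGES I patients with a history of delirium will have abnormalities on the cortical physiology measures". On control of confounding, B.2.3 (Project 5, Aim 3 Analyses) says three things:

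- On design, it claims a match: "Participants will be matched by gender and age between the groups with and without delirium".
- On the model, it names four further covariates, with neither sex nor age among them: "Additional statistical adjustment will be made for index surgical procedure, baseline cognitive function, comorbidity, and vascular risk".
- On the varying timing of the measurements, it says: "we will incorporate time since the index hospitalization as a covariate in the model".

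The sampling is described in B.1.2. All SAGES I patients with delirium are approached, together with "a sample of the non-delirious frequency-matched to the delirious on general cognitive performance (GCP) and age". The comparison group is drawn to resemble the delirium group on a propensity score "taking into account SAGES I baseline GCP, age, and their interaction". A.3.2 gives the same factors, and B.1.3 (Project 2, Aim 3) again describes these 148 patients as matched for age and baseline GCP. Sex appears in none of the three.

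Two general statements bear on sex. B.2.2 says that each project will allow for it in stratified analyses and in modelling, and C.3 plans gender-stratified analysis in all projects. Project 1 Aim 2 (B.2.3), on the same 148 patients, lists both age and gender as control variables.

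**The concern.** The covariate list in Aim 3 is introduced as additional to the matching. Gender and age are left off it because the preceding sentence treats them as settled by design. For age that is correct. For gender it is not, on any account of the sampling that the protocol gives. An analyst who follows the Aim 3 text literally would fit the delirium contrast with sex neither balanced by design nor adjusted for.

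At stake is whether a difference in a TMS or EEG measure between the two groups partly reflects their sex mix. The protocol also gives two different control sets for one cohort, in Project 1 Aim 2 and in Project 5 Aim 3, with no reason for the difference.

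**Working it through.** **The plan's own figure.** B.1.3 says that N=128 "is sufficient to provide 80% power to detect a between-group difference of 0.53 standard deviation (SD) units". For a two-sample t-test at two-sided 0.05:

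| Per group | Detectable difference at 80% power | Power at 0.53 SD |
|---|---|---|
| 64 | 0.50 SD | 0.845 |
| 57 | 0.53 SD | 0.801 |
| 74 | 0.46 SD | 0.893 |

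The 0.53 SD reproduces with about 57 per group, that is 114 of 128, or 11% loss. B.1 says that the computations allow for attrition, so the figure is not in dispute. It serves here only as a yardstick.

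**The sections side by side.**

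| Factor | Matched, per Project 5 Aim 3 | Matched, per A.3.2, B.1.2 and B.1.3 | In the Aim 3 covariate list |
|---|---|---|---|
| Sex | yes | no | no |
| Age | yes | yes | no |
| Baseline GCP | not named | yes | yes, as baseline cognition |

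Only sex is claimed as matched in Aim 3, absent from the sampling description and absent from the covariate list. The matching pilot in B.1.2 reports balance for GCP, age and the Charlson index, and nothing for sex.

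**Chance imbalance in sex.** Inputs: 74 per group, and 58% female in SAGES I (C.3). Assumption: 58% applies in both groups and sex is unrelated to delirium.

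- SD of the difference in proportion female = √(2 × 0.58 × 0.42 / 74) = 0.081.
- Mean absolute imbalance = 0.081 × √(2/π) ≈ 0.065, or 6.5 percentage points.
- 95% range = ±1.96 × 0.081 = ±0.159, or about 16 points either way.

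**Shift in the contrast** = imbalance × sex effect. The protocol gives no sex effect on the physiology measures, so 0.2 to 0.5 SD is assumed.

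- At 6.5 points: 0.065 × 0.2 = 0.013 SD to 0.065 × 0.5 = 0.033 SD.
- At 16 points: 0.16 × 0.2 = 0.032 SD to 0.16 × 0.5 = 0.080 SD, which is 6% to 15% of 0.53 SD.

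A real association of sex with delirium would add to this. The protocol gives no figure for one.

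**Age.** In the pilot, the standardized difference in age fell from 0.29 to -0.04 (-0.16 to 0.09) after matching. Delirium is the exposure, so this is a matched cohort. Leaving a balanced matching factor out of the model does not by itself bias the contrast by delirium history. It gives up precision, and it leaves no correction if those who actually attend for TMS-EEG differ in age between the groups.

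**The case against.** The strongest reply is that sex is not forgotten. B.2.2 and C.3 bind every project to consider it, so Aim 3's list merely fails to repeat a general rule, and a full covariate list is commonly left to a statistical analysis plan. This stands in part: a reader might infer that sex is wholly uncontrolled, and the documents do not support that. But Aim 3 does more than stay silent. It names a gender match, builds its covariate list on it, and so gives the analyst a reason to leave sex out. The general rule and the specific model text need to agree.

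A second reply is that gender could be added when comparators are selected. B.1.2 speaks of matching on age and other factors in specific cases, B.2 gives the data core the task of matching for substudies, and the non-delirious pool is at most 285 + 141 = 426 (Project 4). That is possible, but the sections that define this sample set out the propensity model in full, without sex.

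Two stronger readings also fail. A reader might infer that omitting age biases the comparison; age is matched under both descriptions and was well balanced in the pilot. A reader might also infer that a further match on gender would break the power statement because it uses all 128 patients; the 0.53 SD already corresponds to about 57 per group, so that does not follow.

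**Conclusion.** The point holds as an internal contradiction with a consequence for the model. Project 5 Aim 3 relies on a gender match that the described sampling does not provide, and its own plan then controls sex neither by design nor by covariate. This rests on the text alone and needs no assumption.

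The size does rest on assumptions. With 58% female in both groups and a sex effect of 0.2 to 0.5 SD, even a 16-point chance imbalance moves the contrast by only about 0.03 to 0.08 SD. That is modest beside 0.53 SD. It does not threaten the aim, but it is avoidable. The age omission is a matter of precision and of robustness to selective participation. The change is worth making because the design statement is incorrect as it stands, the covariate list depends on it, and the remedy costs almost nothing.

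**What to change.** In B.2.3, Project 5, Aim 3 Analyses, replace the matching sentence and the covariate sentence with text to this effect: the comparison group is frequency-matched to the delirium group on a propensity score from baseline GCP, age and their interaction (B.1.2) and is not matched on sex; models adjust for sex, age, baseline GCP, type of index surgery, comorbidity, vascular risk and time since index hospitalization.

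This brings Aim 3 into line with A.3.2, B.1.2 and B.2.2, and with the inclusion of age and gender in Project 1 Aim 2. A GCP-by-age term in the outcome model is optional. If a gender match was in fact intended at selection, A.3.2 and B.1.2 should say so instead; sex and age can still be listed as covariates.

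The cost is an edit to two sentences and about two model degrees of freedom. Both variables are already used as controls in this cohort, so no new data are needed.
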